***A Study to Measure Pain Perception Following De-
Epithelialized Free Gingival Graft Harvesting.***

Study Protocol & Statistical Analysis Plan

NCT03895476

January 23, 2023

[name], MS, Principal Investigator

University of Alabama at Birmingham

Birmingham, AL 35294

A Study to Measure Pain Perception Following De-Epithelialized Free Gingival Graft Harvesting.

05/06/2020

1. Study Protocol 1. Objectives/Specific Aims:

The purpose of this study is to compare the effect of a hemostatic collagen sponge, a collagen sponge sealed with a bio-adhesive material, a Platelet rich fibrin and a physical barrier(stent) on the palatal donor sites with the purpose of minimizing postoperative pain after epithelialized gingival graft harvesting.

2. Materials and Method:

Study population:

A total of 80 patients seeking treatment at the UAB SOD Graduate Periodontology clinics will be recruited to participate in this study. The potential candidates will be approached during the treatment planning and/or pre-surgical visit in the periodontal clinic. The investigator/research staff will give the information sheet to the potential participants, explain the study and obtain the patient demographics if the patient participate in the study.

Conventional oral impressions will be made to fabricate a customized acrylic stent for the patient who will receive palatal stent.

This study will conduct a survey using the (VAS) Visual Analog Scale of the postoperative pain following the (FGG) Free Gingival Graft procedure technique with four different methods for coverage of the palatal donor site and evaluating differences in the patient painkiller consumption and willingness to repeat the surgery in the future. On the day of the surgical procedure participants will be given copies of a pain survey (Visual Analog Scale) to be filled every day for two weeks (14 days). The participants will receive a reminder phone call daily to complete the survey. The completed survey (VAS) forms will be collected/returned to the research staff on the day of their follow-up visit.

Study Group:

1: Collagen Plug + Sutures (CPS)

2: Collagen Plug with cyano-acrylate (CPC)

3: Platelet-rich Fibrin (PRF) + sutures

4: Palatal Stent (PS)

3. Study Background:

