This study will evaluate the postoperative pain following the EGG technique with four different methods for coverage of the palatal donor site. The control group will not be protected with any material. Test group 1 will be protected with Platelet rich Fibrin (PRF) while the test group 2 will consist of collagen protection with the additional layer of cyanoacrylate surgical glue. Test group 3 will consist of collagen protection with the application of a physical barrier (Stent) to cover the donor area.

4. Statistical Analysis

Patients' demographics and clinic characteristics at baseline will be summarize with descriptive statistics such as mean, standard deviation (SD), frequency, and proportion where appropriate. The group comparisons at baseline will be conducted with analysis of variance (ANOVA) or Fisher's exact test. Outcome variables – number of analgesics consumed and need for additional analgesics – will be summarize as median and range in each group and the group comparisons will be conducted with Kruskal-Wallis's test followed by post hoc Bonferroni-corrected Wilcoxon rank-sum tests. All the other outcome variables including pain score, swelling level, amount of bleeding, activity tolerance, and the need for additional analgesics will be summarize with mean \pm SD, and analyzed using a general linear mixed regression model to account for the repeated measures. Similar general linear mixed regression models will also use to explore the associations between outcome variables and graft length, width, area, and thickness. All analysis will be conducted using SAS 9.4 (Cary, NC, USA) under the significance level of 0.05.

Visual Analog Scale (VAS)

[figure not shown]
Subject ID #: _____

Site: _____

Date: _____

Please circle a number for each:

1. Pain

[figure not shown]
2. Swelling

[figure not shown]
3. Bleeding

4. Activity Tolerance Scale

5. Did you need to take more painkillers due to palatal pain? Total No. of pills: _____

6. Will you do this surgery again?

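### The SAP gives need for additional analgesics two mutually exclusive analyses, and form item 5 leaves the scope of the pill count open

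*Combined protocol and SAP*

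**What the plan says.** Section 4 sorts the outcomes into two lists.

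- The first names "number of analgesics consumed and need for additional analgesics". These "will be summarize as median and range in each group" and are compared by Kruskal-Wallis with post hoc Bonferroni-corrected Wilcoxon rank-sum tests.
- The second opens "All the other outcome variables including pain score, swelling level, amount of bleeding" and continues "activity tolerance, and the need for additional analgesics will be summarize with mean" ± SD, with a general linear mixed model "to account for the repeated measures".

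Need for additional analgesics is therefore in both lists.

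On the daily form, the only item in the supplied text that could feed the two analgesic outcomes is item 5: "Did you need to take more painkillers due to palatal pain? Total No. of pills". Section 2 (Materials and Method) says that the form is "to be filled every day for two weeks (14 days") and gives "evaluating differences in the patient painkiller consumption" as one of the study's comparisons.

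**The concern.** The second list is defined as whatever the first leaves out, so an outcome cannot belong to both. The two sentences are not framed as a main and a supporting analysis. An analyst following the SAP would have two p-values for one outcome and no rule for preferring either, so the choice could be made after the results are seen.

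A second, smaller question is what the pill count measures. Item 5 asks about needing more painkillers for palatal pain and then gives one blank for a total. The first part points to extra pills and the second to all pills. If patients differed in how they read it, the count could not be separated into its parts afterwards, and painkiller consumption is a comparison the study sets out to make.

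**Working it through.** The SAP gives no figure for this outcome to reproduce. The check is a comparison of the two assignments, followed by two small illustrations.

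**1. The two assignments side by side**

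| | First list | Second list |
|---|---|---|
| Summary | median, range | mean ± SD |
| Analysis | Kruskal-Wallis, then Wilcoxon pairs | general linear mixed model |
| Data used | one value per patient | repeated daily records |
| Multiplicity | Bonferroni | none stated |

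- Records: 80 patients × 14 days = up to 1,120 for the mixed model. For the rank test the SAP does not say how 14 daily answers become one value.
- Multiplicity: four groups give 4 × 3 / 2 = 6 pairs, so the Bonferroni threshold is 0.05 / 6 = 0.0083. The second list states no correction.

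**2. Does either summary suit a daily yes/no?** Assume equal arms of 20 (80 / 4; the allocation ratio is not stated) and a single day.

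- 2 of 20 yes: 10%, median 0, range 0–1, mean 0.10, SD 0.31.
- 9 of 20 yes: 45%, median 0, range 0–1, mean 0.45, SD 0.51.

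Median and range do not distinguish 10% from 45%. The tests do: Kruskal-Wallis p = 0.014, comparison of means p = 0.012. On a single day the weakness is therefore in the descriptive summary, and the two tests nearly agree. The mixed model has a different weakness, because it assumes normal errors for a 0/1 response.

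**3. Can the two analyses differ over 14 days?** The data set below is constructed and is not a prediction. Yes-days per patient is a reduction chosen for this check, since the SAP gives none.

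- Arm A: 6 patients with 14 yes-days, 14 with 0. Mean = (6 × 14) / 20 = 4.2; median 0.
- Arms B, C and D, each: 16 patients with 4 yes-days, 4 with 5. Mean = (16 × 4 + 4 × 5) / 20 = 4.2; median 4.
- Every arm has 4.2 / 14 = 30% yes-days.
- Four-arm Kruskal-Wallis: H = 9.18, p = 0.027.
- Linear mixed model on daily 0/1 with a patient random intercept: difference 0, p = 1.0.
- The SAP's post hoc step, A v B Wilcoxon (asymptotic): p = 0.0226; × 6 = 0.136. Arms C and D are identical to B, so no pair is significant after correction.

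The omnibus rank test and the mixed model can thus fall on opposite sides of 0.05, but the full rank procedure names no differing pair here.

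**4. Item 5 against the two analgesic outcomes**

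- If the blank means all pills, it supplies the number consumed, and the question before it supplies need. The number of additional pills is then not recorded.
- If the blank means only the extra pills, nothing else in the supplied text records the number consumed.

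The printed wording does not settle which applies.

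**The case against.** **The double listing may be a drafting slip that deleting one mention would cure.** That may be so, but nothing in the text shows which mention is the slip. If the answer is yes/no, keeping either one leaves an unsuitable analysis.

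**The two analyses need not differ much.** This stands in part. They nearly agree in the single-day example, and the 14-day example is contrived. A reader might infer that the two analyses can give opposite results. The example does not support that: it shows a significant omnibus test against a zero mean difference, with no reversal of direction and no significant pair after correction.

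**Item 5 has a plain reading.** The question maps to need and the total to number consumed, one to one with the SAP, and a total ordinarily means everything. This is a fair reading, and there is no evidence that patients split between readings. A reader might infer that the pill counts are uninterpretable, or inflated by some multiple. The documents do not support either, since any such multiple would depend wholly on an assumed number of other pills per day.

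**The reference for more painkillers may be given elsewhere.** This stands. Section 2 says that an information sheet is given to participants; it is not in the supplied text, and a yes/no box may have been lost from the form. Neither absence is counted as an error. Such instructions would not by themselves settle what the total covers, and they would not touch the SAP conflict.

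**Conclusion.** The SAP conflict is certain: it can be read directly in two consecutive sentences of section 4. It affects one outcome, for which the plan offers two analyses with different data structures, different handling of multiplicity and possibly different significance, and no rule of precedence. That neither suits the outcome depends on its being a daily yes/no, which the wording of item 5 suggests but the supplied form does not confirm.

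The item 5 point is secondary and held with moderate confidence. The wording allows two readings of the count; whether patients differed in practice is unknown.

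No between-arm bias and no loss of power is claimed. The change should be made, because the outcome bears on a stated comparison and the repair is cheap.

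**What to change.** **SAP**

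- Remove need for additional analgesics from both lists and name one analysis: a repeated-measures binary model of the daily yes/no (GEE or mixed logistic).
- State a fallback in case the model fails to converge or data are sparse, such as a rank test on each patient's proportion of completed days answered yes.
- Keep Kruskal-Wallis for the number of analgesics consumed. Say how daily counts become one value per patient and how missing daily forms are handled.

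**Form, if still in use.** Split item 5 into three parts:

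- total painkiller pills that day;
- whether additional pills were needed for palatal pain (yes/no), with the reference taken from the study's own analgesic instructions;
- if yes, how many.

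**Form, if already collected.** The protocol is dated 05/06/2020 and the combined document January 23, 2023, so this is possible. In that case make the SAP change and report the scope of the pill count as uncertain.

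**Cost.** A short SAP edit and, where still possible, a reprinted form. The binary model may meet sparse-data problems at about 20 per arm (assumed), hence the fallback. Forms completed under the existing wording would need a version flag.
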